Study Title: Outcomes of sclerotherapy of the ulcer bed compared to a combination of ablation and injections

Principal Investigator: [name]

Sub Investigator: [name], PhD

Background:

Venous ulcers are the most common cause of ulcerations that affect the lower extremities and are estimated to effect 1% of the American population¹. They are responsible for more than 80% of lower extremity ulcerations²⁻⁴. Venous ulcers are most common in the elderly and in patients with a history of diabetes, obesity, varicose veins, blood clots, and edema of the lower extremities. Treatment is extensive averaging 6 to 12 months of continual therapy. Healing rates for these ulcers are poor and more than 50% of these types of ulcers are still unhealed after 9 months^{5,6}. Over 70% of those patients will end up developing another venous ulcer within 5 years¹. With these astounding numbers, it is imperative for early diagnosis and prompt treatment. Any underlying causes should also be assessed and determined at the time of diagnosis to help with healing and prevention.

Management of these ulcers has historically been compression treatment, stripping of the superficial veins, elevation of the effected leg, and exercise. Ablative superficial surgery along with compression is another form of treatment. Endovenous ablation is where the problematic vein is sealed off (generally the great saphenous vein (GSV) in the thigh or the short saphenous vein (SSV) behind the knee and calf). A catheter is fed up the vein from the ankle or knee level. It is carefully fed, using the aid of ultrasound, to the junction between the GSV and SSV. An electrical current or laser energy is passed through the vein wall causing the vein to contract and seal itself off. This procedure is quicker and less painful compared to the traditional operation of vein stripping. Early endovenous ablation of superficial venous reflux in addition to compression has resulted in shorter ulcer healing time and a reduction in the 12-month reoccurrence rate versus compression therapy alone^{7,8}.

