This will be a randomized clinical trial. Subjects will be randomly allocated to each group. There will be roughly equal number of subjects in each arm. Arm 1 will be patients receiving sclerotherapy and ablation at the start of treatment along with compression therapy. The patients in arm 1 will not receive any further treatment during the duration of the study. Arm 2 will be patients who receive sclerotherapy at the start of treatment along with compression therapy, and ablation 3 months later. All patients in arm 2 will receive ablation at their 3 month appointment. After ablation, the patients in arm 2 will not receive any further treatment for the remainder of the study.

30 opaque envelopes, 15 indicating arm 1 and 15 indicating arm 2, will be prepared by the study coordinator. Patients who agree to participate will select an envelope and treatment will be initiated based off of the arm that is selected. In the event of a participants early termination from the study, up to 5 study participants will be replaced in each study arm to help ensure an adequate number of subjects for analysis. The purpose of this study is to see if one treatment is more effective over the other in treating chronic venous ulcers.

Patients who participate will have ultrasound-guided sclerosant injected into the affected area. Half of the patients will only receive injections (arm 2) while the other half of the patients will receive injections along with ablation (arm 1). Patients in arm 1 will not receive any further

treatment during the remainder of the study. All patients will fill out a quality of life questionnaire (using the VEINES-QOL/Sym questionnaire) and complete the venous clinical severity score (VCSS) questionnaire prior to treatment. All patients will undergo compression therapy.

Patients will be seen weekly after treatment. Safety assessments will take place during these weekly appointments to ensure patient safety. After 3 months, patients will be brought in for another follow up visit. The 3 month follow up is considered standard protocol after these procedures to monitor for adverse events. Ulcer size, symptoms, healing rate, quality of life (using the VEINES-QOL/Sym questionnaire), and venous clinical severity score (VCSS) will be assessed. All patients in arm 2, will receive ablation at this time.

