All patients will continue to be seen weekly to assess healing progress and to ensure patient safety. Six months following initial treatment, the patients will return for another follow up visit where ulcer size, symptoms, healing rate, quality of life (using the VEINES-QOL/Sym questionnaire), and VCSS will be assessed. Participation in the study will be complete after the 6 month follow up appointment. Patients will continue to see their physician for treatment, if needed, after their participation has concluded.

All treatments and appointments are considered standard of care and will be billed to the patients insurance.

Following completion of data collection (see study variables on attached excel sheet), analysis will be completed to identify study results. We will be analyzing the differences between the two groups in A. ulcer healing rate (comparison of means, generalized linear model), and B. proportion of healed ulcers (Chi square).

Inclusion/Exclusion Criteria

Inclusion Criteria:

- Patients 18 years of age and older
- Patients who have saphenous vein reflux and a single venous ulcer of any size

Exclusion Criteria:

- Patients under 18 years of age
- Patients with multiple venous ulcers

How Human Subjects will be involved

All enrolled subjects will have ultrasound-guided sclerosant injected into the affected area. At the start of treatment, half of the patients will receive injections at the start of treatment and ablation 3 months later (arm 2) while the other half of the patients will receive injections in addition to ablation at the start of treatment (arm 1). All patients will undergo compression therapy following treatment.

Risks/Side-effects

During the **sclerosant injections**, some people experience minor stinging or cramps when the needle is inserted into the vein. The risks associated with the injection include, but are not limited to, bruising, raised red areas, small skin sores, darkened skin in the form of lines or spots, and multiple tiny red blood vessels. These side effects usually go away within a few days to several weeks. Other more serious side effects include, but are not limited to, inflammation, blood clot, air bubbles and allergic reaction.

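### Eligibility does not require that a patient can receive every component of both arms before the envelope is drawn, so unsuitability for ablation can surface at different times in the two arms and can bias the month-3 comparison

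*Combined protocol and SAP*

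**What the plan says.** The Inclusion/Exclusion Criteria section has two inclusion lines: "Patients 18 years of age and older" and "Patients who have saphenous vein reflux and a single venous ulcer of any size". The two exclusions mirror them: age under 18 and more than one venous ulcer. No line concerns fitness for any study treatment.

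Three treatments are planned for everyone:

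- **Injection.** How Human Subjects will be involved gives ultrasound-guided sclerosant to all enrolled subjects.
- **Compression.** Methods states: "All patients will undergo compression therapy".
- **Ablation.** Methods gives it to arm 1 at the start. For arm 2 it says: "All patients in arm 2 will receive ablation at their 3 month appointment". No exception is stated.

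On allocation, Methods says: "Patients who agree to participate will select an envelope and treatment will be initiated based off of the arm that is selected". On patients who do not continue, Methods and Number of Subjects say: "In the event of a participants early termination from the study, up to 5 study participants will be replaced in each study arm". Early termination is not defined. The planned analyses are a comparison of means with a generalized linear model for healing rate, and a chi-square test for the proportion healed. No analysis population is given, and nothing says how a patient whose allocated ablation is not given will be handled.

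**The concern.** In a randomised comparison, a patient should be able to receive either arm before the arm is known. Here the timing of ablation is the randomised contrast, so a patient who turns out to be unsuitable for it is likely to be identified at different times. In arm 1 the question arises at once. In arm 2 it need not arise until month 3.

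Two consequences are possible, depending on handling that the protocol leaves open. If such patients are terminated and replaced in arm 1, that arm becomes a group selected for suitability while arm 2 at month 3 is unselected. If they stay in arm 1 without ablation, the contrast between the arms is diluted. Month 3 matters because it is the only scheduled outcome assessment before arm 2 is ablated.

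There is also a safeguard question. Risks/Side-effects says of the injections: "Other more serious side effects include, but are not limited to, inflammation, blood clot, air bubbles and allergic reaction". Background describes venous ulcers as most common in the elderly and in patients with a "history of diabetes, obesity, varicose veins, blood clots, and edema of the lower extremities". No criterion takes up either statement, so the protocol does not itself prevent enrolment of a patient who cannot safely receive a study treatment.

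**Working it through.** **The plan's own figure.** Number of Subjects allows up to 40. With 15 per arm and up to 5 replacements per arm, 2 × 15 + 2 × 5 = 40, which agrees. The documents give no alpha, power, effect size or expected healing proportions, so 15 per arm cannot be checked further.

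**Which components can produce a difference between arms.** Injection and compression start together in both arms, so unsuitability for either surfaces at the same time in both. Only ablation differs in timing.

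**Inputs.** From the documents: 15 per arm, up to 5 replacements per arm, ablation at the start (arm 1) or month 3 (arm 2). Assumed, because the documents do not give them: p, the share of eligible patients unsuitable for ablation; h_s and h_u, the month-3 healing proportions in suitable and unsuitable patients; g = h_s − h_u.

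**Case A: unsuitable patients are removed and replaced in arm 1 but counted in arm 2 at month 3, with no treatment effect.**

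- Arm 1 heals at h_s.
- Arm 2 heals at (1 − p)h_s + p·h_u.
- Difference = h_s − [(1 − p)h_s + p·h_u] = p(h_s − h_u) = p × g, favouring arm 1 if g is positive.

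| p | h_s | h_u | g | p × g |
|---|---|---|---|---|
| 5% | 50% | 40% | 10 | 0.5 points |
| 10% | 60% | 30% | 30 | 3 points |
| 20% | 60% | 30% | 30 | 6 points |
| 20% | 60% | 20% | 40 | 8 points |
| 30% | 70% | 20% | 50 | 15 points |
| any | equal | equal | 0 | 0 |

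Over p from 5% to 30%, h_s from 50% to 70% and h_u from 20% to 40%, the range is 0.5 to 15 points.

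**Case B: unsuitable patients stay in arm 1 unablated and all are analysed as allocated.** If early ablation changes healing by D in those who receive it, and they make up a share (1 − p) of arm 1, the month-3 contrast is (1 − p) × D. It is 0.90 D at p = 10% and 0.80 D at p = 20%. This is dilution, not selection bias.

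**Month 6.** If unsuitable arm 2 patients also leave at month 3, a month-6 comparison of completers has lost them from both arms and the p × g term largely disappears. If they stay in arm 2 unablated, it does not.

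**Is the situation likely at this size?** The chance of at least one unsuitable patient among 15 is 1 − (1 − p)^15: 54% at p = 5%, 79% at 10%, 96% at 20%. The expected number is 15p: 0.75, 1.5 and 3. One patient is 1/15 = 6.7 points of an arm's healed proportion.

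**Scale against sampling error.** With 15 per arm, the standard error of a difference in proportions is √(2h(1 − h)/15): √(0.42/15) = 16.7 points at h = 30% or 70%, and √(0.50/15) = 18.3 points at h = 50%. A bias of 3 to 8 points is 0.45 to 1.2 patients in 15, well inside that error.

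**The case against.** The strongest objection is that screening probably happens. Methods says patients treated at the institute are evaluated for possible enrolment and only those who qualify are approached. The protocol calls all treatments standard of care, and the reflux criterion already requires a refluxing saphenous vein, which is part of suitability for ablation. This has weight, but it does not close the gap. Qualifying points back to the same written criteria, the content of the evaluation is not described, and reflux alone says nothing about injection, compression or the rest of suitability for ablation.

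A reader might infer that unsuitable patients do leave arm 1 on day 0 and do remain in arm 2 until month 3. The documents do not say so. Early termination is never linked to failure to receive ablation, and such patients might be screened out, kept unablated, or withdrawn. The bias needs removal in arm 1, retention in arm 2 and a different prognosis.

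A reader might also infer that patients with known contraindications are exposed. That is not supported either. The documents list side effects and describe the general ulcer population, but they name no contraindications.

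Finally, p and g are assumed. A larger figure, such as 25% × 40 = 10 points, treats all 5 replacements out of 20 arm 1 patients as due to ablation unsuitability, although replacement is allowed for any early termination. It should not be read as an expected value.

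**Conclusion.** The gap is real and its consequence is conditional. The criteria do not require that a patient can receive both arms, no suitability check is written before allocation, and ablation falls at different times in the two arms. With replacement allowed and no analysis population defined, selection after allocation is possible and would fall mainly on month 3.

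Under the assumptions shown, the spurious month-3 difference is p × g, with 3 points at p = 10% and g = 30 as a moderate example, and zero if prognosis is equal. If unsuitable patients are kept unablated, the contrast shrinks by (1 − p) instead. On safety, the supportable statement is that the protocol does not prevent enrolment of patients who cannot safely receive a study treatment; actual exposure is not shown. This is a worthwhile, inexpensive improvement and not a flaw that invalidates the trial.

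**What to change.** 1. Add an inclusion criterion along these lines: *before an envelope is opened, the treating physician has documented that the patient is a candidate for sclerosant injection, endovenous ablation and compression, and could be treated in either arm.* Add the mirror exclusion. Which conditions bear on candidacy is for the investigator to define.
2. State in the analysis text that all randomised patients are analysed as allocated, including those whose allocated ablation is not given, and that their outcomes continue to be collected where they agree. Replacements are added to the originals and not substituted for them. This is needed as well as the criterion, because ablation may still be refused or become unsuitable after allocation.

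With the check in place, p among randomised patients is close to zero, and so are p × g and the dilution from this source. The cost is two criterion lines, one checklist item before allocation and a short addition to the analysis section. The target of 15 per arm and the ceiling of 40 do not change. The downside is that a few patients are screened out before allocation, which slightly narrows the population.
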